### **6.2.2 Handling of Missing Data**

#### **6.2.2.1 Imputation**

Severity Symptom Score: Missing values on severity symptom score will not be imputed. However, where a patient has died, their symptom score will not be considered missing, but will be imputed with the maximum severity score (3) for each symptom at each time point.

Clinical Outcome Scale: Missing values on clinical outcome scale will not be imputed. However, where a patient has died, their clinical outcome scale will not be considered missing, but will be imputed with maximum clinical outcome scale (7 [maximum severity if alive] or 8 [maximum severity if dead]) at each time point.

Viral load: Prior to the log 10 transformation, non-numeric viral load results reported as below the limit of detection will be replaced by the limit of detection divided by 2. As an example, results reported as “<2228cp/mL SARS-CoV2 detected” will be replaced by 1114 cp/mL. Non-numeric viral load results reported as “No SARS-CoV2 detected” will be replaced by 1 cp/mL. Replacing by 1 (instead of by zero) will be done so that the log 10 of viral load will be defined in all subjects (and equal to zero when no SARS-CoV2 is detected).

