### 4.1. Inclusion Criteria

Patients must satisfy all of the following criteria unless otherwise stated:

1. Willing and able to provide informed consent
2. Male or female patients > 18 years of age on the day of informed consent
3. Have received a confirmed diagnosis of COVID-19 (positive for SARS-CoV-2), as assessed by PCR or point-of-care within 72 hours of first dose on Day 1
4. Have mild to moderate signs or symptoms of COVID-19 with onset within 5 days of first dose on Day 1, at least two of the following symptoms:
  - stuffy or runny nose
  - sore throat
  - shortness of breath
  - cough
  - fatigue
  - myalgia
  - headache
  - chills or shivering
  - feeling hot or feverish
  - nausea
  - vomiting
  - diarrhea
  - anosmia
  - ageusia
5. Outpatient with COVID-19 disease (not requiring oxygen therapy [WHO COVID-19 Clinical Improvement Ordinal Scale, score of 3])
6. Patient is aware of the investigational nature of this study and willing to comply with protocol treatments, blood tests, and other evaluations listed in the ICF.

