#### **4.3. Disease Diagnostic Criteria**

Patients with SARS-CoV-2 infection confirmed (nasal, nasopharyngeal, oropharyngeal, or respiratory samples, not serology testing, or patients with pre-study confirmed PCR test) and mild to moderate symptoms related to COVID-19 disease are required for enrollment.

The entry testing is performed locally based on testing methods available at the site, such as PCR or rapid antigen test, to confirm the presence of SARS-CoV-2 in a person with symptoms compatible with COVID-19. Both saliva (Oragene) collection and self-collection of mid-turbinate nasal swab under supervision of a healthcare professional (virtual or home visit) will also occur at Screening/Baseline, Day 1, Day 3, Day 5, Day 7, Day 10, and Day 28.

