- a. Screening/Baseline assessments may all be performed on the same calendar day and should be performed at the study site or as a home visit within 72 hours of first dose. Baseline assessments that are also performed at Screening do not need to be repeated if on the same calendar day. Study drug should be dispensed at the Screening/Baseline visit and only taken after the Day 1 virtual visit confirming the positive COVID-19 test has occurred. If the PCR test is negative or laboratory results exclude the patient, they will not take the first dose of study drug and be withdrawn from the study.
- b. Patients will be randomized to receive either 900, 1800, or 3600 mg of dalcetrapib treatment or placebo.
- c. The entry testing is performed locally based on testing methods available at the site, such as PCR or rapid antigen test.
- d. Patients must have at least two mild to moderate signs or symptoms of COVID-19, as described in the inclusion criteria, with onset within 5 days of first dose on Day 1. Symptoms will be assessed daily for the first 10 days, then at Day 14 and Day 28 and as clinically indicated.
- e. Dates of change in WHO scale status between visits will be recorded over the course of the 28-day study period.
- f. SARS-CoV-2 viral loads will be obtained by both saliva (Oragene) and mid-turbinate nasal swab self-collected under supervision of a healthcare professional at Screening/Baseline, Day 1, Day 3, Day 5, Day 7, Day 10, and Day 28.
- g. Two PK samples will be collected on Day 10, one at predose and one at postdose in a sampling window of 0-2, 2-4, 4-6, 6-10, or 10-24 hours postdose. Patients will be evenly randomized to one of the sampling windows on Day 10.
- h. Study drug is self-administered as once daily oral tablets on Days 1 to 10.
- i. In case of screen failure only.

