## 1 INTRODUCTION

The purpose of this statistical analysis plan (SAP) is to present the statistical methodology that will be used for the final analysis of DalCor Pharmaceuticals DAL-401. This plan also provides a description of the tables, figures and listings that will be included in the final statistical report. It is based on the protocol dated 22-OCT-2020 and on the annotated case report form (CRF) version 1.0. In case of differences in terms of descriptions or explanations between the SAP and the clinical protocol, the SAP will supersede the protocol. Any deviation to this SAP would be reported in the statistical report.

Since the protocol was developed and discussed with the regulatory authorities, a greater understanding of COVID-19 and clinical trials in COVID-19 has emerged. New variants have also been observed and their clinical course needs to be taken into consideration. Based on this emerging knowledge, a higher emphasis will be placed on viral load analyses when interpreting the data and deciding on POC in this study. Less emphasis will therefore be placed on the current primary endpoint of Patient Reported Outcomes and endpoints that look at changes in symptoms of COVID-19. Certain symptoms such as loss of taste and loss of smell as well as cough are chronic symptoms which may not resolve over the course of a 28-day study. In view of this the endpoints evaluating symptoms will not include taste, smell or cough in some analyses.

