#### **3.1 Intent-To-Treat (ITT) Population**

The Intent-To-Treat Population will include all participants who were randomized [a randomization number is provided in the eCRF Form “Randomization”] and received at least 1 dose of study drug [as confirmed in the eCRF Form “Study Drug Administration”] and not reported as a screen failure [in the eCRF Form “Disposition-Study Completion” ]. Participant data will be summarized by treatment assigned.

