#### **6.4 Efficacy Analysis**

The analysis of treatment efficacy will be based on the Intent-to-Treat Population. The PP population will be used for sensitivity analysis. This section is a summary of the planned efficacy analyses of the most important efficacy endpoints including primary and key secondary efficacy endpoints.

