### 6.4.3 Other Secondary Analysis

#### **6.4.3.1 Time to Viral Clearance Based on PCR Test for SARS-CoV-2**

Each subject will be tested to determine if the subject has COVID-19 by obtaining a PCR or rapid antigen test as it confirms the presence of SARS-CoV-2. A subject will be considered to no longer have COVID-19 if two consecutive PCRs do not detect SARS-CoV-2. Time to viral clearance using PCR test for SARS-CoV-2, as assessed using the saliva and using the nasal swab, will be calculated as date of the first negative PCR test for SARS-CoV-2 – date of randomization + 1. Subjects who did not obtain two consecutive negative PCRs will be censored at the date of study completion.

Same statistical methods as those described in section 6.4.1 will be used to analyze the time to viral clearance.

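### Viral-load analyses include patients with no virus detected at baseline, which dilutes any antiviral effect by roughly the (unknown) share of such patients

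*SAP*

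**What the plan says.** **Role of viral load.** SAP 1 states that "a higher emphasis will be placed on viral load analyses when interpreting the data and deciding on POC in this study". In SAP 2.2 and 4.2, change in log10 viral load is a key secondary endpoint and time to viral clearance is an other secondary one. AUC is analysed under the key secondary heading (6.4.2.2).

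**Who is analysed.** SAP 6.4: "The analysis of treatment efficacy will be based on the Intent-to-Treat Population". Under SAP 3.1 that set is everyone randomised who "received at least 1 dose of study drug" and was not a screen failure. Detectable virus at baseline is not a condition.

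**Coding.** SAP 6.2.2.1 replaces a result with no virus detected by 1 cp/mL. The reason given is "so that the log 10 of viral load will be defined in all subjects (and equal to zero when no SARS-CoV2 is detected". A result that is detected but below 2228 cp/mL becomes 1114 cp/mL.

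**Entry test and endpoint sample.** Protocol 4.3: "The entry testing is performed locally based on testing methods available at the site, such as PCR or rapid antigen test". Protocol 4.1 requires a positive diagnosis "as assessed by PCR or point-of-care within 72 hours of first dose on Day 1". The endpoint uses self-collected saliva and nasal swabs tested centrally (Protocol 7.1.4, 7.1.5), each specimen analysed separately (SAP 4.2). Baseline is the Day 1 sample, or Screening if Day 1 is missing (SAP Appendix 2).

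**Models.** The change model adjusts for baseline and baseline-by-visit (SAP 6.4.2.1). The AUC model contains treatment only (6.4.2.2). For clearance, 6.4.3.1 says: "A subject will be considered to no longer have COVID-19 if two consecutive PCRs do not detect SARS-CoV-2". The event is dated at the first negative, counted from randomisation. Neither a positive baseline nor a post-dose start is required.

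**The concern.** The entry test and the baseline sample differ in timing, collection and laboratory. A patient can therefore qualify on the local test and have no virus detected in the central saliva sample, the central swab, or both. In that specimen:

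- The change from baseline cannot be negative.
- The AUC starts at the floor, with no baseline term to account for it.
- Clearance can be recorded at or before the first dose.

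None of this depends on the arm, so the effect is to pull the arms together. The proposed mechanism is inhibition of viral replication, and viral load is given more weight in the proof-of-concept judgement. The risk is therefore of missing a real antiviral effect and stopping development wrongly.

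**Working it through.** **No planned figure to reproduce.** The documents give no power, SD or detectable difference for any viral-load endpoint. The 127 events with 80% power in SAP 6.1 concern symptom resolution. That figure does reproduce under the protocol's group-sequential design: interim at 73 of 127 events, stop above HR 1.45, futility below HR 1, final one-sided 0.186, power 80.04%. It says nothing about viral load.

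**What the SAP's rules do to one patient undetected at baseline**

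- Baseline log10(1) = 0, so every change is at least 0.
- One later detected result below 2228 cp/mL gives log10(1114) − 0 = +3.05.
- Clearance time = date of first negative − date of randomisation + 1. Randomisation falls 1 to 2 days before Day 1. Negatives on Day 1 and Day 3 give 1 + 1 = 2 or 2 + 1 = 3 days, dated on the day of first dose. If Screening and Day 1 count as separate tests, a negative on the randomisation date gives 0 + 1 = 1 day, before the first dose.

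**Shrinkage and power in closed form.** Let f be the share undetected at baseline in both arms. If they stay at the floor, the mean difference becomes about (1 − f) times its value in detected patients. For the two highest doses against placebo, 104 vs 52, the standard error in SD units is √(1/52 + 1/104) = 0.170. At two-sided 0.20, 80% power needs (1.282 + 0.842) × 0.170 = 0.36 SD. Keeping everyone uses 0.36 × (1 − f) at full n; excluding uses 0.36 at n × (1 − f). Power, kept vs excluded:

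- f = 5%: 76.9% vs 78.5%
- f = 10%: 73.5% vs 76.8%
- f = 20%: 66.2% vs 73.2%
- f = 30%: 58.1% vs 69.0%

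This gives every patient the same SD, which is crude: patients who stay at the floor contribute little residual variation once baseline is in the model.

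**Simulation of the planned analyses** (3,000 trials per share). Assumptions, none from the documents except the sample sizes and the 0.20 level: baseline in detected patients mean 6, SD 1.5 log10; fall to Day 10 of 2.5, SD 1.4; extra fall on drug 0.5; placebo clearance rate 0.08 per day with HR 1.4; undetected patients stay at 0 and all count as cleared on Day 1. Power is the chance of a favourable result, all ITT vs detected at baseline.

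| f | Change estimate, all ITT | (1 − f) × −0.475 | Change model power | AUC power | Clearance log-rank power |
|---|---|---|---|---|---|
| 0 | −0.475 | −0.475 | 79.3% | 35.1% | 59.5% |
| 5% | −0.453 | −0.451 | 75.2 vs 78.1% | 30.9 vs 35.0% | 53.0 vs 55.4% |
| 10% | −0.424 | −0.428 | 70.9 vs 74.7% | 26.9 vs 34.3% | 50.8 vs 55.3% |
| 20% | −0.387 | −0.380 | 69.0 vs 73.4% | 22.8 vs 31.8% | 43.5 vs 50.8% |
| 30% | −0.328 | −0.333 | 61.1 vs 66.8% | 19.1 vs 29.4% | 37.2 vs 48.1% |

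Among detected patients the change estimate stays at −0.47 to −0.48. The power gaps are 3 to 6 points (change), 4 to 10 (AUC) and 2 to 11 (clearance).

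**Sensitivity of the change model.** A Day 5 version (2,000 trials; fall 2, SD 1.5; effect 0.6) varied how low follow-up results split between the two codes. With undetected patients staying at 0, the gap was 0 to 4 points at f = 5%, 0 to 3 at 10%, and 0 to 5 at 30%. It reached about 10 points only when 15% of undetected patients were assumed to rise to 1114 cp/mL.

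**The case against.** **Prevalence may be low.** Entry needs a positive test within 72 hours and symptom onset within 5 days. Footnote a to Protocol Table 5 adds: "If the PCR test is negative or laboratory results exclude the patient, they will not take the first dose of study drug". This stands as a limit on numbers, but it does not close the gap. The footnote concerns confirmation of the positive COVID-19 test, and nothing ties it to the central saliva or swab baseline. Its wording is loose, because the entry test may be an antigen test.

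**The coding rule proves nothing about baseline.** A value for undetected results is needed at follow-up anyway. Correct: a reader might infer that the SAP expects many negative baselines, and it does not say so.

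**The change model already adjusts for baseline.** This stands in part. Adjustment removes much of the added noise, so the power loss is modest, but the estimate still shrinks. The AUC and clearance analyses have no such adjustment.

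**Counting all undetected patients as Day 1 events is a worst case.** This stands. Two negatives are needed and some patients will turn positive. Appendix 2 also merges Screening and Day 1 into one baseline; if clearance uses those visits, Day 3 must be negative too. The date then still falls on Day 1.

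**The dilution is conservative.** It does not create false positives. In a proof-of-concept trial, though, a missed effect is also a costly error.

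**Excluded patients are informative.** A reader might infer that patients without baseline virus say nothing about the drug. That goes too far: preventing a rise from undetected is relevant to a replication inhibitor. Full ITT should therefore be kept as supportive.

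**Conclusion.** The gap is real. No section restricts any viral-load analysis to patients with virus detected in that specimen at baseline, and the clearance rule allows an event at or before the first dose. The bias is toward no difference, with estimates shrinking by roughly the undetected share.

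The size is uncertain because the documents do not give that share. Under assumed shares of 5–30%, the power loss is:

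- about 0–10 points for the change model (0–6 if undetected patients stay undetected);
- about 7–10 points for AUC at shares of 10–30%;
- about 2–11 points for clearance if all undetected patients count as early events.

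If the share is near zero, so is the loss.

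A reader might conclude that viral load alone decides proof of concept. The SAP says only that it gets more emphasis; the primary endpoint remains symptom resolution.

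**What to change.** Before unblinding, amend the SAP:

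1. **6.4.3.1:** restrict time to clearance, separately for saliva and swab, to ITT patients with virus detected in that specimen at baseline. Require the first negative of the pair to be dated after the first dose.
2. **6.4.2.1 and 6.4.2.2:** name the ITT subset with virus detected at baseline in that specimen (Day 1, or Screening if Day 1 is missing) as the main analysis of change and AUC. Keep full ITT as supportive.

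The cost is SAP wording and one flag per specimen, using data already collected. The lead viral-load tables will have fewer patients, and the saliva and swab subsets will differ. Any effect on rises from an undetected baseline will show only in the supportive ITT analysis. The comparison stays randomised provided that Day 1 samples were taken before dosing. The SAP says they were to be, but Appendix 2 classifies them by date alone, so state this as an assumption.

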#### **6.2.2.2 Censoring**

Severity Symptom Score: For time to resolution, a patient will be censored if the patient has not had the required time point assessment if not due to death. If patient has died or received another antiviral therapy prior to the assessment endpoint, then the patient will be considered as having a moderate or severe COVID-19 symptom for all COVID-19 symptoms and imputed to maximum severity score at the assessment day.

Viral Clearance: For time to viral clearance, a patient will be censored if the patient has not had the required time point assessment.

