### **4.4.2. Discontinuation of Study Treatment**

Study medication will be discontinued for the following reasons:

- Patients whose screening labs indicate an eGFR <50mL/min using CKD-EPI will discontinue study medication and be followed for safety
- Withdrawal by patient (patient is free to discontinue at any point of time; specify reason of discontinuation in the eCRF)
- At the discretion of the Investigator for safety, behavioral, or administrative reasons
- Lack of efficacy (e.g., patients who require nonstudy antiviral or anticytokine therapy due to progression of COVID-19). Note: Study medication would be discontinued upon worsening of symptoms requiring hospitalization, in such cases patients could receive remdesivir
- Adverse event

Study will be discontinued for the following reasons:

- Withdrawal of consent (patient is free to discontinue at any point of time; specify reason of discontinuation in the eCRF)
- Sponsor determination
- Unexpected safety concerns
- Medical or ethical reasons affecting the continued performance of the study
- Difficulties in the recruitment of patients

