### **6.2. Prohibited Medications**

Simultaneous participation in other clinical treatment study protocols is not allowed.

Treatment with any antiviral drugs expected to have activity against SARS-CoV-2 are not allowed during therapy with study treatment but may be used as rescue medications. Orlistat results in lowered serum levels of dalcetrapib and is not allowed as this may result in decreased efficacy.

Patients who begin to receive nonstudy rescue antiviral medication for COVID-19 after the start of study treatment will be discontinued from study treatment, they will remain in the study and complete all follow-up assessments.

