### **4 EFFICACY ENDPOINTS**

#### **4.1 Primary Efficacy Endpoint**

The primary efficacy endpoint is:

- Time to sustained clinical resolution of symptoms (excluding cough, sense of smell and taste)

Sustained clinical resolution is defined as occurring when no key COVID-19 related symptom (excluding cough, sense of smell and taste) has a score higher than 1 over a 72-hour period (as documented using an electronic patient-reported outcome [ePRO] instrument or in the eCRF). The time to resolution will be taken as the time from randomization until the first day of the last 72-hour period where the patient meets the definition of resolution within 28 days. Patients who do not meet the definition of resolution 28 days after randomization will be considered not resolved.

The classification of sustained clinical resolution of symptoms (excluding cough, sense of smell and taste) follows similar steps as the algorithm presented in Appendix 1.

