##### **6.4.1 Primary Analysis**

The primary endpoint is time to sustained clinical resolution of symptoms (excluding cough, sense of smell and taste) as determined by symptom score. Sustained clinical resolution of symptoms (excluding cough, sense of smell and taste) is defined in Section 4.1. Time to sustained clinical resolution will be calculated as date of resolution – date of randomization + 1. Subjects who did not resolve will be censored at the last time point where they were not resolved [see Section 9 Appendix 1]. The number and percentage of patients whose symptoms resolved will be presented, and to summarize the time to resolution, censored subjects will be imputed with a time to resolution of 29 days and simple medians with 80% confidence intervals will be provided.

The differences in time to sustained clinical resolution of symptoms (excluding cough, sense of smell and taste) between the treatment groups will be evaluated using 2-sided log-rank tests. The combined two highest treatment groups will be compared to placebo in addition to the comparison of individual doses.

The cumulative incidence curve for sustained clinical resolution (excluding cough, sense of smell and taste) will also be presented using 1 – Kaplan-Meier estimates(Section 7, Figure 2). Should there be several deaths, the cumulative incidence curve will be presented under a competing risk model.

A listing with the score of each symptom at each time point will be provided (Section 7, Listing 7).

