## 9 APPENDICES

### APPENDIX 1

Algorithm used to classify sustained clinical resolution:

For each subject, all ePRO records will be sorted by the date/time. For each assessment, we characterize the record as clinically resolved (i.e., score of 0 for taste and smell and all other symptoms, a score of 0 or 1) or not.

From Day1 to Day10 (or last ePRO assessment before Day14)

- a) If resolved at Day 10 (or last ePRO assessment), identify first date when resolution occurred with no relapse. This is the tentative date of resolution to be confirmed at Day 14 and Day 28.
- b) If not resolved at Day 10 (or last ePRO assessment), re-assess at Day 14.

At Day14:

- c) If resolved for the first time at Day 14 (i.e. was not resolved at Day 10 or before), use date of Day 14 as the tentative date of resolution to be confirmed at Day 28.
- d) If still resolved at Day 14 (i.e. was already resolved at Day10 or before), use date of resolution identified in step a). This is the tentative date of resolution to be confirmed at Day 28.
- e) If not resolved at Day 14, re-assess at Day28.

At Day28:

- f) If resolved for the first time at Day 28 (i.e., was not resolved at Day 14), subject will be classified as resolved within 28 days and date of resolution will be the date of Day 28.
- g) If still resolved at Day 28 (i.e. was already resolved at Day 14), subject will be classified as resolved within 28 days and date of resolution will be the date of resolution identified in step c) or d).
- h) If not resolved at Day 28, subject will be classified as not resolved within 28 days and the date of censoring will be the date of Day 28.

It should also be noted that subjects who do not have an assessment at Day 28 will be classified as non-resolved REGARDLESS if symptoms were resolved up to their last assessment. Date of censoring will be the date of study discontinuation.

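### SAP 6.2.2.2 and SAP Appendix 1 give opposite primary outcomes for a patient rescued with an antiviral who then recovers, and nothing links the two rules

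*SAP*

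**What the plan says.** **The failure rule.** SAP 6.2.2.2, repeating Protocol 8.8.2, covers time to resolution. "If patient has died or received another antiviral therapy prior to the assessment endpoint", the patient counts as having moderate or severe symptoms throughout and is "imputed to maximum severity score at the assessment day". For deaths, SAP 6.2.2.1 adds that the maximum score is used at each time point. It has no matching statement for rescue.

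**The derivation.** SAP 4.1 says the primary endpoint "follows similar steps as the algorithm presented in Appendix 1". SAP 6.4.1 says "Subjects who did not resolve will be censored at the last time point where they were not resolved" and points to Appendix 1. Neither section refers to 6.2.2.2. Appendix 1 works from scores: "For each assessment, we characterize the record as clinically resolved" or not. Its Day 28 step reads "If still resolved at Day 28 (i.e. was already resolved at Day 14), subject will be classified as resolved within 28 days". The only exception not based on scores is a missing Day 28 assessment, which makes the patient non-resolved and censored at study discontinuation.

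**Rescue in the protocol.** Protocol 6.2 stops study treatment in patients who start rescue antivirals, but "they will remain in the study and complete all follow-up assessments". Protocol 4.4.2 illustrates lack of efficacy, as a reason to stop study drug, by "patients who require nonstudy antiviral or anticytokine therapy due to progression of COVID-19".

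**The concern.** Two rules in the same SAP decide whether a rescued patient is an event in the primary analysis, and they can disagree. The disagreement can arise in practice. Protocol 4.4.2 foresees that patients hospitalized for worsening could receive remdesivir, and Protocol 6.2 keeps patients on rescue antivirals under observation, so real post-rescue scores will exist and may be good ones. Two programmers who each follow a stated rule could then produce different primary datasets from the same trial. Appendix 1 also drives the key secondary endpoint (resolution of all symptoms) and, by similar steps, the complete-resolution endpoints. If the choice between the rules is left until the data are unblinded, it can be made knowing which way it moves the result.

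**Working it through.** **1. One patient under both rules.** Take a patient who starts a non-study antiviral on Day 6 and scores as resolved from Day 9 through Day 28.

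- Appendix 1 on recorded scores: tentative resolution on Day 9 (step a), still resolved on Day 14 (step d) and on Day 28 (step g). The patient is an event dated Day 9.
- 6.2.2.2, read as overwriting every assessment after rescue: not resolved at Days 10, 14 and 28 (steps b, e, h). The patient is censored at Day 28.
- 6.2.2.2, read as overwriting Day 28 only: step h again gives not resolved.
- 6.2.2.2, read as overwriting a single earlier visit such as Day 7: the run from Day 9 is untouched and the patient is an event dated Day 9.

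The first two readings of 6.2.2.2 are the natural ones and give failure. The third does not, and the text does not exclude it, because neither the assessment endpoint nor the assessment day is defined.

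**2. Deaths.** Appendix 1 never turns a death into a resolution, because a missing Day 28 assessment means non-resolved. It does censor at study discontinuation. Under 6.2.2.1 and 6.2.2.2 the patient has imputed maximum scores at the assessments, so Day 28 is not missing and step h censors at Day 28. The outcome is the same but the time at risk differs.

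**3. Is the order of steps implied elsewhere?** SAP 6.4.4 states that last observation carried forward is done before the algorithm is applied. No such instruction ties 6.2.2.2 to Appendix 1.

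**4. The plan's own power figure.** Inputs (Protocol 8.1, SAP 6.1): 127 events, HR 1.4, alpha 0.2, 104 active versus 52 placebo. By Schoenfeld, power = Φ(ln HR × √(d × 1/3 × 2/3) − z).

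- ln 1.4 × √(127 × 2/9) = 0.3365 × 5.312 = 1.788.
- One-sided 0.2: Φ(1.788 − 0.842) = 0.828. Adding the interim look at 73 events (power-family boundary, ρ = 2) and the futility stop at HR 1 gives 0.800, the stated 80%.
- Two-sided 0.20, the level in SAP 6.2: Φ(1.788 − 1.282) = 0.694.

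The simulated powers below use the two-sided level, so they start near 68% and not at 80%.

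**5. Size under assumed rescue rates.** Simulated log-rank tests: 52 versus 104 patients, exponential times with 80% of placebo resolved by Day 28, HR 1.4, assessments on Days 1–10, 14 and 28, rescue independent of resolution. Rescued patients are either not resolved at Day 28 (failure rule) or resolved at Day 14 (Appendix 1).

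| Rescue, placebo/active | Expected rescued patients | Failure rule | Appendix 1 |
|---|---|---|---|
| 4% / 2% | 0.04×52 = 2.1; 0.02×104 = 2.1 | 73% | 67% |
| 4% / 4% | 2.1; 4.2 | 63% | 68% |
| 8% / 8% | 4.2; 8.3 | 59% | 67% |
| 2% / 4% | 1.0; 4.2 | 55% | 67% |

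Repeat runs differ by a few points (for example 55% to 59% in the last row, failure rule), but the direction in each row does not change. A separate simulation, one-sided at 0.2 with rescued patients keeping their own resolution times under Appendix 1, shows the same pattern: 0.72 versus 0.81 at 10%/10%, and 0.88 versus 0.82 at 10%/5%.

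**The case against.** The strongest reply is that the rule exists. SAP 6.2.2.2 opens by naming time to resolution and sits in a general section that need not be repeated in every derivation. It says which score a rescued patient receives, and Appendix 1 then says how scores are classified. Read together, antiviral-rescued patients fail. This stands as far as it goes: a reader might infer that the SAP has no rescue rule, or that treatment failures will enter the analysis as successes, and the documents support neither. What they show is a live rule with no link to the algorithm and no clear statement of which records it overwrites.

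A reader might also infer that the protocol defines anticytokine therapy as treatment failure. It does not. Protocol 4.4.2 gives it as an example of a reason to stop study drug, while Protocol 8.8.2 names only death and another antiviral as endpoint triggers. Widening the trigger is an estimand choice, not the correction of an error. What stands is that the failure rule is silent on anticytokine therapy.

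Finally, the SAP Introduction puts less weight on symptom endpoints than on viral load when judging proof of concept. That lowers the stakes, but sustained resolution of symptoms remains the designated primary endpoint.

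**Conclusion.** The point holds as an inconsistency in how the primary endpoint is derived. For a patient rescued with an antiviral who recovers and stays in follow-up, Appendix 1 gives an event and 6.2.2.2, on its natural readings, gives a failure. For deaths the two places agree on non-resolution but not on the censoring day.

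The size is unknown because no rescue rate is given. In the assumed scenarios the gap in power is about 5 to 12 percentage points, and it rests on only a handful of rescued patients. It goes in both directions: the failure rule raises power when rescue is twice as common on placebo, and lowers it when rescue is balanced or more common on active. It would be wrong to assume that balanced rescue makes the choice unimportant, since at 8% in each arm the gap is 67 − 59 = 8 points. These figures depend on exponential times, on rescue being unrelated to resolution, and on rescued patients resolving at Day 14 under Appendix 1. The reason to act is a single, reproducible primary endpoint, not more power.

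**What to change.** Before unblinding:

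- **Appendix 1.** Add a first step that applies 6.2.2.2 before any record is classified. From the date of death or of first non-study antiviral therapy, every later record to Day 28 counts as not resolved, and the patient goes to step h, censored at Day 28 (nominal Day 28 if there is no visit). Keep the existing antiviral trigger. Limiting it to antivirals given for progression would narrow the current rule and require a judgement for each medication.
- **SAP 6.2.2.2.** Replace the reference to the assessment day by every later assessment, and cite Appendix 1. Cite 6.2.2.2 in 4.1 and 6.4.1.
- **Scope.** Apply the same step to all resolution endpoints, and state that it takes precedence over the carry-forward in 6.4.4.
- **Anticytokine therapy.** The sponsor should reconcile Protocol 4.4.2 with Protocol 8.8.2 and SAP 6.2.2.2. A sensitivity analysis counting anticytokine therapy as failure would be enough.

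The cost is a few SAP sentences, a list of the coded drugs that count as triggers, and a merge with concomitant-medication data, for which Protocol 6.1 already requires dates and reason for use. Patient care and data collection do not change.
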